14.1 Sample Size Determination

The sample size will be of 30 patients completing the study. 15 patients will be included in the experimental treatment arm (Group A) and 15 patients in the active-comparator arm (Group B) to allow an adequate comparison between treatments.

Dropped patients during the course of the study will be replaced.

The sample size of 15 patients per arm is sufficient for planned descriptive analyses and 95% confidence intervals of efficacy.

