14.8.2 Secondary Endpoints

The secondary endpoints of the study are:

- Proportion of patients achieving hemostasis at TBS (absence of bleeding) at 2 (for sFilm-FS product only), 3, 5, 7 or 10 minutes following first product application, without the occurrence of re-bleeding starting from 10 minutes after product application and until the completion of surgical closure.
- Incidence of re-treatment (one or more additional patch of sFilm-FS or TACHOSIL[®]) at the TBS at the different time points (2 for sFilm-FS, 3, 5, 7, 10 minutes from first product application).
- Time to Hemostasis from first product application (TTHP). Time to Hemostasis from patient randomization (TTHR) will be collected as well but will not be used as endpoint.
- Percentage of total patients (patients that achieved hemostasis with a single patch application and patients that required additional patches) that have achieved hemostasis 10 minutes after first product application and therefore did not need to convert to standard of care treatment at the end of these 10 minutes.
- Incidence of treatment failure, based on pre-defined treatment failure criteria (see definition in Section 11.1.3 of the protocol).
- Incidence of transfusion requirements in the 6 months follow up period.

Descriptive efficacy analyses will be summarized separately by treatment arm.

Primary analyses will calculate the proportion of patients achieving hemostasis at 3 minutes among the sFilm-SF treatment arm. With 15 patients randomized to sFilm-SF, reasonable confidence intervals (CI) can be estimated. For example, if 80% of the patients achieve hemostasis at 3 minutes (similar to a TACHOSIL[®] reported values of 81% for this endpoint), the accompanying 95% confidence interval (CI) is 52% to 96% (using exact confidence limits). This CI provides evidence that greater than 52% of patients with similar conditions will achieve hemostasis at 3 minutes. This will also be reported for the 15 patients randomized to the TACHOSIL[®] arm. There will be no formal comparison between the two-arms.

Similarly, proportions of patients and corresponding 95% CIs will be estimated for all of the following, separately by treatment arm:

- achieving hemostasis at TBS at each remaining time point,
- incidence of re-treatment (separately by time),
- incidence of treatment failure (as defined in Section 11.1.3), and
- incidence of transfusion requirements.

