6.13.1 Proportion of Patients achieving Hemostasis at TBS

For each patients achievement of hemostasis at TBS (absence of bleeding) at 2 (for sFilm-FS product only), 3, 5, 7 or 10 minutes following first product application will be derived. No occurrence of re-bleeding starting from 10 minutes after product application and until the completion of surgical closure must happen.

This variable, as being a time-profile in the efficacy response, will be considered to suggest a superiority in the efficacy of study drug versus control treatment. Since this is an exploratory proof of concept study and no hypothesis of extent in the difference between treatment groups a priori has been defined, we estimate the differences in the proportion of patients achieving at each time points hemostasis at TBS by the calculation of the exact 95% confidence interval (Clopper-Pearson exact method, considering the sample size) at each time point. This measure gives also a precision of the difference between treatments observed.

Beside Clopper-Pearson confidence intervals number and percentage of patients achievement of hemostasis at TBS will be tabulated by time point. The tabulation will also differ between first application and re-applications.

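### SAP 6.13.1 drops the lead status of the protocol's 3-minute sFilm-FS hemostasis proportion and reads the time profile for superiority, and SAP section 9 does not list the change

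*SAP*

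**What the plan says.** **Protocol.** Section 14.8.2 ranks the efficacy analyses: "Primary analyses will calculate the proportion of patients achieving hemostasis at 3 minutes among the sFilm-SF treatment arm". It illustrates the precision with an exact interval for the case "if 80% of the patients achieve hemostasis at 3 minutes", set beside TACHOSIL's "reported values of 81% for this endpoint". For the comparator it adds "This will also be reported for the 15 patients randomized to the TACHOSIL[®] arm", and then "There will be no formal comparison between the two-arms". The remaining time points follow in the same form, arm by arm. Section 14.5 specifies estimation with exact intervals and no hypothesis tests. Section 14.1 justifies the size on that footing: "The sample size of 15 patients per arm is sufficient for planned descriptive analyses and 95% confidence intervals of efficacy". Section 14.6 requires the SAP to set out changes from the original statistical plan.

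**SAP.** Section 6.13.1 names no leading time point, and no other section does so. Its estimand is between-arm: "we estimate the differences in the proportion of patients achieving at each time points hemostasis at TBS". It says the hemostasis variable, viewed as a time profile, "will be considered to suggest a superiority in the efficacy of study drug versus control treatment". Section 6.13 says that the intervals presented for efficacy are those on treatment differences, without p-values. Section 6.1 provides Clopper-Pearson intervals for percentages only where judged appropriate. Section 9.1 records the renamed and added analysis sets and states that none of FAS1, FAS2 and PPS leads. Section 9.2 records only the added analysis of time to hemostasis from randomization.

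**The concern.** The protocol commits in advance to one efficacy figure by which the product will first be described. The SAP leaves that figure unranked among several time points and three analysis sets, no longer clearly commits to its exact single-arm interval, and announces a directional reading. A reader who checks section 9 for departures from the protocol would not learn of any of this.

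The trial is open-label and hemostasis is the surgeon's judgement, so a lead estimate fixed beforehand is one of the few protections against choosing the most flattering result for the report. Without it, whichever interval looks best could be put forward as a hint of superiority.

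**Working it through.** **1. The protocol's own figure.** Inputs from protocol 14.8.2: 80% of 15, so x = 12, n = 15. Clopper-Pearson limits:

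- lower = Beta quantile(0.025; x, n - x + 1) = Beta(0.025; 12, 4) = 0.519
- upper = Beta quantile(0.975; x + 1, n - x) = Beta(0.975; 13, 3) = 0.957

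This gives 51.9% to 95.7% and reproduces the stated 52% to 96%. It is an interval for one proportion in one arm.

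**2. What 15 per arm says about a difference.** Newcombe interval, with d = p1 - p2 and Wilson limits (l, u) for each arm:

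- lower = d - sqrt[(p1 - l1)^2 + (u2 - p2)^2]
- upper = d + sqrt[(u1 - p1)^2 + (p2 - l2)^2]

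The Wilson limits are 0.548 to 0.930 for 12/15 and 0.796 to 1 for 15/15.

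- 12/15 v 12/15: 0 ± sqrt(0.252^2 + 0.130^2) = ±0.283, so -28 to +28 points.
- 15/15 v 12/15: lower = 0.200 - sqrt(0.204^2 + 0.130^2) = -0.042; upper = 0.200 + 0.252 = 0.452. So -4 to +45 points, which still includes zero.

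**3. How many contrasts are open.** SAP 6.13.1 lists 2, 3, 5, 7 and 10 minutes, but 2 minutes is assessed for sFilm-FS only. That leaves 4 shared time points. With three unranked sets there are 4 x 3 = 12 contrasts.

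**4. Chance of a favourable interval when the arms are equal.** Assumptions, none of them in the documents except where noted:

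- 15 per arm in FAS2 (the size is from the protocol).
- One cumulative hemostasis profile shared by both arms.
- Random losses of 10% for FAS1 and 20% for PPS, nested and unrelated to outcome.
- Newcombe 95% CIs.

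There were 100,000 simulated trials per row. Cells give the percentage of trials with at least one interval excluding zero in favour of sFilm-FS, with either direction in brackets.

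| Assumed % at 3/5/7/10 min | 3 min, FAS2 | Any of 4, FAS2 | Any of 12 |
|---|---|---|---|
| 80/90/95/98 | 2.5 (4.9) | 3.4 (6.7) | 4.5 (8.8) |
| 81/87/91/94 | 2.4 (4.8) | 3.8 (7.6) | 4.9 (9.7) |
| 60/75/85/93 | 2.5 (4.9) | 5.7 (11.4) | 8.2 (16.1) |
| 50/65/80/90 | 2.2 (4.5) | 6.2 (12.5) | 9.2 (18.4) |

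The first two rows start from the protocol's own 3-minute rates (80% and 81%); the later values are assumed. Full enumeration of the single contrast gives 2.3% to 2.5% in favour (4.6% to 5.0% in either direction) at 3-minute rates of 50%, 60%, 80% and 81%.

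With smaller set losses (3% for FAS1, 7% for PPS), any-of-12 runs from 3.7% (7.6%) in the first row to 7.5% (15.4%) in the last.

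**5. Whether the named method fits.** SAP 6.13.1 names Clopper-Pearson for the difference between arms. That method gives limits for a single binomial proportion. It suits the protocol's single-arm figure and does not yield an interval for a difference of two proportions.

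**The case against.** Much of the case for the SAP stands.

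- The 3-minute result is not lost. Section 6.13.1 still tabulates numbers and percentages by time point, section 6.13 summarises by treatment group, and section 6.13.3 gives Kaplan-Meier incidence at 3 minutes. A reader might infer that the SAP removes the figure. It removes the figure's lead status and the clear commitment to its exact interval.
- A reader might also infer that the SAP adds the formal comparison that the protocol rules out. The text does not show that. There is no test and no p-value, section 6.6 treats every result as exploratory, and 6.13.1 itself says that no difference was hypothesised in advance. A descriptive interval on a difference is not clearly a formal comparison, and protocol 7.2 and 14.1 themselves expect the two arms to be compared.
- All time points and all three sets are to be reported, which limits outright suppression, and section 9.1 openly declares that no set leads.
- The either-direction percentages overstate the risk at issue. About half of those intervals would favour TACHOSIL, so the one-directional figures are the relevant ones.

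What remains is narrower. The sentence on superiority does not fit a descriptive trial of 15 per arm, the lead time point has gone, and section 9 mentions neither although protocol 14.6 requires such changes to be set out. Complete reporting does not settle which figure will be put first.

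**Conclusion.** The point holds as an undeclared departure from the protocol's ranking of its secondary efficacy analyses, together with an unsupported superiority reading. It does not touch the primary endpoint.

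The size is moderate. The chance of a spurious interval in favour of sFilm-FS rises from about 2.3% to 2.5% for the one pre-specified contrast to about 4% to 9% when any of 12 may be put forward; in either direction, from about 5% to about 9% to 18%. The low end applies if 3-minute hemostasis is near the protocol's 80% to 81%, the high end if it is nearer 50%. All of this rests on the assumed profiles and set losses in the working.

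A reader might quote a figure near 16% as the risk of a false superiority claim. That figure counts both directions and needs a 3-minute rate of about 60%, well below the rates that the protocol cites.

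**What to change.** In SAP 6.13.1:

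- State that the lead efficacy analysis is the 3-minute hemostasis proportion in the sFilm-FS arm with its Clopper-Pearson 95% CI, on one named analysis set, shown beside the same figure for TACHOSIL. FAS1 corresponds to the population that protocol 14.2 calls primary for efficacy; choosing another set would be a further change to list.
- Label the other time points, the other sets and all between-arm differences as supportive and descriptive.
- For the differences, name an interval method valid for two independent proportions, such as Newcombe's.
- Delete the sentence on suggesting superiority.

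In SAP 6.13, make clear that per-arm exact intervals are presented as well as intervals on differences. In SAP section 9, list the between-arm differences as an addition to the protocol.

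The cost is a few sentences before database lock, with no new data. The small downside is that the sponsor gives up the option of leading with another time point or set.

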6.13.2 Incidence of Re-Treatment

Incidence of re-treatment (defined as one or more additional patch of sFilm-FS or TACHOSIL®) at the TBS at the different time points (2 for sFilm-FS, 3, 5, 7, 10 minutes from first product application) will be tabulated with counts and percentages. Differences in incidences between treatment groups will be estimated by Clopper-Pearson 95% confidence intervals for each time point.

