The time of application will be considered **TP-01** and will be recorded as such. If the sFilm-FS is to be used, do not moisten the product prior to application, as the product will be activated immediately. TACHOSIL® should be used in accordance with the approved Prescribing Information.

Following product application, manual compression will be applied and will be maintained for at least 2 minutes for sFilm-FS and for at least 3 minutes for TACHOSIL®, until examination of TBS. The Investigator may use a surgical sponge (laparotomy pad or surgical gauze) to assist in providing adequate pressure to stem all bleeding over the entire treated surface area at the TBS. Hemostasis will then be assessed by carefully releasing manual compression and removing the surgical sponge (if used) without disturbing the hemostasis product. The product unit should be left in place once it adheres to organ tissue.

In case hemostasis is not achieved within 2 minutes (for sFilm-FS) or 3 minutes (for TACHOSIL®), the surgeon will wait 2 additional minutes applying additional pressure on the gauze before carefully releasing manual compression and checking again.

Hemostasis will be assessed at 2 (for sFilm-FS only), 3, 5, 7 and 10 minutes following product application. These time points will be recorded as **TP-02**, **TP-03**, **TP-05**, **TP-07** and **TP-10** respectively.

Re-treatment: If the surgeon is not satisfied with the placement of the patch, or if hemostasis is not achieved, or if during the subsequent observation period bleeding requiring treatment recurs, the

Investigator may decide to apply an additional product unit as specified above. In this case, the already applied product unit should not be removed, unless it did not adhere to the TBS.

The time point of product re-application will be recorded as **TPR-01**. After re-treatment application, manual compression must be applied for at least 2 (for sFilm-FS) or 3 minutes (for TACHOSIL®, as described above. Hemostasis will then be assessed following product re-application at any time-points within the original 10 minutes observation period (**TPR-02**, **TPR-03** or other) and until site closure. A minimum of 5 minutes observation period at the TBS has to take place before site closure. The time followed by 5-minutes observation period to assess hemostasis will be recorded.

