12.2. Secondary Endpoints

The secondary endpoints of the study are:

- Proportion of patients achieving hemostasis at TBS (absence of bleeding) at 2 (for sFilm-FS product only), 3, 5, 7 or 10 minutes following first product application, without the occurrence of re-bleeding, starting from 10 minutes after product application and until the completion of surgical closure.
- Incidence of re-treatment (one or more additional patch of sFilm-FS or TACHOSIL[®]) at the TBS at the different time points (2 for sFilm-FS, 3, 5, 7, 10 minutes from first product application).
- Time to Hemostasis from first product application (TTHP). Time to Hemostasis from patient randomization (TTHR) will be collected as well but will not be used as endpoint.
- Percentage of total patients (patients that achieved hemostasis with a single patch application and patients that required additional patches) that have achieved hemostasis 10 minutes after first product application and therefore did not need to convert to standard of care treatment at the end of these 10 minutes.
- Incidence of treatment failure based on pre-defined treatment failure criteria (see definition in Section 11.1.3 of the protocol).
- Incidence of transfusion requirements in the 6 months follow-up period.

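### SAP 6.13.2 tabulates re-treatment at fixed minutes without a counting rule, so the arms' different re-check times can create a spurious difference in either direction

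*SAP*

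**What the plan says.** Re-treatment, meaning one or more further study patches at the TBS, is a secondary endpoint. Protocol 12.2 defines its incidence "at the TBS at the different time points (2 for sFilm-FS, 3, 5, 7, 10 minutes from first product application"). Protocol 14.8.2 asks for a proportion and 95% interval per arm for "incidence of re-treatment (separately by time"). SAP 6.13.2 keeps this grid, so that re-treatment "at the TBS at the different time points (2 for sFilm-FS, 3, 5, 7, 10 minutes from first product application) will be tabulated with counts". It then adds a comparison: "Differences in incidences between treatment groups will be estimated by Clopper-Pearson 95% confidence intervals for each time point".

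The timing comes from protocol 11.1.3:

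- Compression lasts at least 2 minutes for sFilm-FS and at least 3 for TACHOSIL.
- If bleeding continues at that check, "the surgeon will wait 2 additional minutes applying additional pressure on the gauze before carefully releasing manual compression and checking again".
- The scheduled checks are given separately: "Hemostasis will be assessed at 2 (for sFilm-FS only), 3, 5, 7 and 10 minutes following product application".
- Re-treatment is at the investigator's discretion. It may follow poor placement, absent hemostasis or recurrent bleeding.
- It has its own time stamp: "The time point of product re-application will be recorded as" TPR-01. First application is TP-01.

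Patch use also appears elsewhere without a time axis: units applied at the TBS (SAP 6.11) and patches per patient (SAP 7). The table shells are in a separate appendix that is not among the documents reviewed.

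**The concern.** Re-treatment happens when the surgeon decides on it, whereas the table has columns only at the hemostasis assessment minutes. The plan gives no rule for placing an event that falls between two columns. It also does not say whether a patient re-treated early still counts in later columns.

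This would be a minor gap if both arms ran on the same clock, but they do not. The compression schedule places the natural re-treatment moments at different minutes in the two arms, and only some of those minutes have a column. A per-minute difference then mixes how often patients were re-treated with when the protocol had the surgeon look. The 2-minute column adds to this, because it exists for one arm only.

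At stake is a named secondary efficacy endpoint with a planned interval on the treatment difference, in an open-label trial. SAP 2 says that the plan is finalised only after the data review meeting, so the counting rule could still be open once the data are known.

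**Working it through.** **The plan's own precision figure.** Protocol 14.8.2 gives an exact 95% interval of 52% to 96% for 80% of 15. Clopper-Pearson limits for 12/15 are 51.9% and 95.7%, which reproduces it. No figure is given for re-treatment.

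**Inputs.** 15 patients per arm (protocol 14.1); first checks at 2 and 3 minutes and a 2-minute wait (protocol 11.1.3); columns at 2 (sFilm-FS only), 3, 5, 7 and 10 (SAP 6.13.2). The documents give no re-treatment rate. I assume that 4 of 15 patients in each arm are re-treated once, so the true difference is zero, and vary this below.

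**Pathway 1: re-treatment after the further wait.** sFilm-FS: 2 + 2 = minute 4, which has no column. TACHOSIL: 3 + 2 = minute 5, which has one.

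| Counting rule | sFilm-FS events fall in | TACHOSIL events fall in | Table shows (sFilm-FS v TACHOSIL) |
|---|---|---|---|
| Exact match | no column | 5 | at 5: 0/15 v 4/15 |
| Next point | 5 | 5 | at 5: 4/15 v 4/15 |
| Previous point | 3 | 5 | at 3: 4/15 v 0/15; at 5: 0/15 v 4/15 |
| Nearest point (tie to the earlier) | 3 | 5 | as previous point |
| Cumulative, by the minute | 5 onward | 5 onward | at 3: 0 v 0; at 5, 7, 10: 4/15 v 4/15 |

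Minute 4 is equally far from 3 and 5. If the tie went to the later point, nearest-point counting would match next-point counting.

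**Pathway 2: re-treatment at the first failed check.** sFilm-FS falls at minute 2 and TACHOSIL at minute 3. Both minutes are columns, so the four non-cumulative rules agree. The sFilm-FS events sit in the 2-minute column, which has no comparator, and the 3-minute column shows 0/15 v 4/15. Cumulative counting shows 4/15 v 4/15 from minute 3 onward.

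**Interval for 0/15 v 4/15.** Clopper-Pearson is an interval for one proportion, so I use Newcombe's method for a difference, built from Wilson limits.

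- Wilson limits: 0/15 gives 0 to 0.204; 4/15 = 0.267 gives 0.109 to 0.520.
- Difference: 0 - 0.267 = -0.267.
- Lower limit: -0.267 - √[(0 - 0)² + (0.520 - 0.267)²] = -0.267 - 0.253 = -0.520.
- Upper limit: -0.267 + √[(0.204 - 0)² + (0.267 - 0.109)²] = -0.267 + 0.258 = -0.009.

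The result is -27 points (-52 to -1). With the arms reversed, as at minute 3 under previous- or nearest-point counting, it is +27 points (+1 to +52). Counted as 4/15 v 4/15, it is 0 (-30 to +30).

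**Other assumed rates, 0 v r of 15:** r = 3 gives -20 points (-45 to +4); r = 5 gives -33 points (-58 to -6).

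**Second re-treatments.** If the wait is repeated, they fall at 4 + 2 + 2 = 8 and 5 + 3 + 2 = 10 minutes. If not, they fall at 4 + 2 = 6 and 5 + 3 = 8. The protocol does not say which applies, so nothing here relies on them.

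**The case against.** The strongest reply is that SAP 6.13.2 never says to drop events that fall between columns. SAP 6.13.3 uses incidence on the same grid for Kaplan-Meier estimates of hemostasis, which are cumulative, and one or more additional patches is a patient-level definition that fits a cumulative count. On that reading there is no problem. This is a fair argument for what the authors may have intended. It does not settle the matter: SAP 6.13.2 does not say so, and the protocol's instruction to report separately by time points the other way.

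The re-treatment times are also constructed. Compression times are minimums, re-treatment is discretionary, and placement problems or re-bleeding can prompt it at any minute. That stands, and it makes the size uncertain. In pathway 2 no first re-treatment is lost, because the sFilm-FS events are visible at minute 2. That also stands, but the planned 3-minute difference is still misleading.

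Units at the TBS (SAP 6.11) would reveal a gross contradiction, although they carry no timing and are not this endpoint. SAP 7 does not separate the TBS from other sites. The shells in the separate appendix might contain an overall row. Finally, SAP 6.6 calls all results explorative and no p-values are planned, so an interval that excludes zero triggers no decision.

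A reader might go further and infer that the table is tilted toward sFilm-FS. The documents do not support that. In pathway 1 the gap vanishes under next-point or cumulative counting, and at minute 3 it turns against sFilm-FS under previous- or nearest-point counting.

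**Conclusion.** The concern holds as an undefined counting rule on a grid that does not match the two arms' re-check times. With equal re-treatment of 4/15 per arm, the same data can show -27, 0 or +27 points at a given column. For re-treatment at the first failed check, every non-cumulative rule tested gives -27 points at minute 3. These sizes assume a common rate of 3 to 5 in 15 and re-treatment exactly at the earliest check times. Actual times will be more scattered, which would dilute the effect.

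The direction is not fixed, so this is not evidence of a bias in favour of the sponsor's product. Nor is overall patch use hidden, since SAP 6.11 and SAP 7 report it. What the plan lacks is an interpretable between-arm comparison for this endpoint. It should be corrected before the SAP is final, because the choice of rule can determine the sign of the reported difference.

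**What to change.** In SAP 6.13.2, replace the point-in-time tabulation with:

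1. **Any re-treatment.** The number and percentage of patients with any additional study patch at the TBS, first within 10 minutes of first application and then up to surgical closure. Give an exact interval per arm, and a between-arm difference with an interval valid for two proportions, such as Newcombe's.
2. **Cumulative re-treatment.** The proportion re-treated by 3, 5, 7 and 10 minutes, from TPR-01 minus TP-01. Use all treated patients as the denominator, not the available observations that SAP 6.1 would otherwise apply. Show the 2-minute figure for sFilm-FS only, with no difference.

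Cumulative figures at early minutes can still differ because the arms are checked at different times: a TACHOSIL re-treatment shortly after minute 5 would miss the 5-minute count. The any-re-treatment row should therefore be the headline.

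Protocol 11.1.3 must also be reconciled with itself. Its 2-minute wait implies an sFilm-FS check at minute 4, which its assessment schedule does not contain, and it does not say whether the wait applies again after re-treatment. How to resolve this is for the clinical team.

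The cost is SAP wording and one re-programmed table. Both times are already collected. The small downside is a cumulative headline in place of a per-minute one.
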